Therapeutic use of amniotic fluid and the amniotic membrane has existed in medicine for decades in many different capacities (Shimberg 1938). Some applications include healing of the eye, soft-tissue wounds, and bone fractures (Karaçal et al. 2005; Kerimoğlu 2008). Recently, amniotic epithelial cells have been shown to express stem cell markers of pluripotency, including octamer-binding protein 4 (*Oct-4*) and *Nanog* (Miki and Strom 2006; Miki 2011). Cells isolated from the amnion are able to differentiate into all three germ layers: endoderm, mesoderm and ectoderm (Toda et al. 2007).

Amniotic fluid and membrane contain mesenchymal stem cells (MSCs), which may be useful in graft material for bone fusion for several reasons. They have been shown to have osteoinductive and osteogenic properties, and therefore can regenerate bone. They have been shown to selectively adhere to bone substrate and are unlikely to be rejected since they are immune privileged (they do not express human leukocyte antigen (HLA) class II molecules). Also, stem cells from amniotic origin have low risk of tumorigenicity (Siegel et al. 2007). Finally,

stem cells from an amniotic source do not pose ethical issues, as there is no risk to the mother or fetus.

NuCel® is a commercially available (NuTech Medical, Birmingham, AL) source of MSCs derived from human amniotic fluid in combination with morselized amniotic membrane tissue. In addition to stem cells, this tissue contains collagen, proteoglycans, hyaluronic acid, trophic proteins including bone morphogenetic proteins (BMPs), and growth factors.

Therefore, the goal of the proposed research is to use NuCel® in the bone graft material applied to patients undergoing posterolateral lumbar spine fusion, to assess its ability to promote bone fusion. Its safety and efficacy will be compared to a standard allograft material routinely used for this surgery.

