## II. METHODS

### *A. Study Population*

Participants will consist of patients presenting with symptomatic, one or two-level lumbar degenerative disc disease, spondylosis or spondylolisthesis. They must have failed traditional conservative treatment measures, such as pain medication, physical therapy, lumbar epidural steroid injections or lumbar bracing support, prior to surgery. They must be candidates for a one or two-level posterolateral lumbar fusion, with instrumentation, with or without laminectomy. The participants are patients that the surgeon would consider as low risk for non-union, and would have received only demineralized bone matrix (DBM) bone graft material without any other graft material, in particular, no recombinant human bone morphogenetic protein (rhBMP-2). Patients who would be considered higher risk of non-union, and who would have typically received rhBMP-2 will be excluded according to the list below.

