### ***B. Hypothesis***

We hypothesize that the NuCel® group will report, on average, Oswestry Disability Index (ODI) scores 10% lower than those of the DBM group. Assuming a baseline ODI score of 52 (SD=8) for the DBM group, 90% power and an a Type 1 error rate of 5%, a sample size of 42 patients (21 per group) would be sufficient to detect a 10% difference between groups using a repeated measures design with 6 measurement points. To account for drop-out, loss to follow-up, and/or refusal to complete study documents at follow-up, we plan to recruit a total of 60 patients (30 per treatment arm).

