## Radiological outcomes

Radiographs of the lumbar spine will be assessed at the time of surgery (intra-operatively) and at 1 and 2 months (anterior-posterior and lateral) and at 3 months (flexion-extension) after surgery to detect any spinal instrumentation failure. CT scans of the lumbar spine will be taken at 6 and 12 months post surgery to assess fusion. Assessment will be performed by an independent radiologist who will be blinded to the treatment and clinical condition of the participants. The radiologist will score fusion according to the following categories: no fusion, any fusion, or solid fusion.

The table below shows the time line for each data collection activity:

|                                              | Pre-op | Intra-op | Post-op months (range in days) |                      |                      |                            |                             |
|----------------------------------------------|--------|----------|--------------------------------|----------------------|----------------------|----------------------------|-----------------------------|
|                                              |        |          | 1
(25-
35
days)       | 2
(55-65
days) | 3
(85-95
days) | 6
(170-
190
days) | 12
(355-
375
days) |
| Oswestry Disability Index (ODI)  | X      |          | X                              | X                    | X                    | X                          | X                           |
| Pain rating scales               | X      |          | X                              | X                    | X                    | X                          | X                           |
| Neurological exam                | X      |          | X                              | X                    | X                    | X                          | X                           |
| CT scan                          |        |          |                                |                      |                      | X                          | X                           |
| X-ray                            |        | X        | X                              | X                    | X                    |                            |                             |

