#### ***E. Statistical Analysis***

We will first compare the demographic and pre-operative clinical characteristics of the NuCel® and DBM groups to evaluate randomization fidelity. If any characteristics are found to be statistically significant between the groups, this will be accounted for in the analyses of the primary and secondary outcomes. We will describe all categorical variables as percentages and continuous variables with means and standard deviations.

To evaluate our primary outcome we will use a linear mixed model with ODI score as the dependent variable and treatment group and time as independent variables. Mixed models are often preferred over a two-way ANOVA because they allow for incomplete data from participants and do not require a strictly normal distribution in the dependent variable. This model will also be used to evaluate the effect of treatment group on pain scores over time. Statistical significance will be set at  $p < .05$ .

We will report the frequency of observed fusion at the 6-month and 12-month follow-up periods via CT scan by treatment group. If our sample size allows, we will compare the NuCel® and DBM groups on fusion rates at each time point using Fisher’s Exact tests. Statistical significance will be set at  $p < .05$ .

We will report the frequency of adverse events experienced by the NuCel® and DBM groups including negative changes in neurological exam (sensory and motor) findings during the follow-up period.

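### Fisher's exact test, the only test named for fusion, is valid but conservative at these arm sizes; a Boschloo test ordered by the two-sided Fisher p-value holds the same 5% limit and never rejects less

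*Combined protocol and SAP*

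**What the plan says.** The Introduction gives the purpose of using NuCel as "to assess its ability to promote bone fusion". Fusion is read from CT at 6 and 12 months by a blinded radiologist in three grades: "no fusion, any fusion, or solid fusion" (section C, Radiological outcomes). Section A selects for good healing: "The participants are patients that the surgeon would consider as low risk for non-union".

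Section E reports fusion frequencies by arm at both visits in any case. The test is conditional: "If our sample size allows, we will compare the NuCel® and DBM groups" on "fusion rates at each time point using Fisher’s Exact tests". The threshold is p < .05; sidedness is not stated.

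The documents give no expected fusion rate, no power for fusion, and no rule for turning three grades into a rate. The primary outcome is the ODI, and the sample size rests on it. Section B says "a sample size of 42 patients (21 per group) would be sufficient" and, to allow for losses, "we plan to recruit a total of 60 patients (30 per treatment arm").

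**The concern.** Fisher's test conditions on both margins of the 2x2 table. With a few dozen patients per arm, few p-values are attainable, and the chance of p < .05 under no difference falls well short of 5%. The shortfall is largest when nearly everyone fuses, and a population chosen for low risk of non-union makes high rates plausible.

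Part of the allowed 5% therefore goes unused in the only inferential comparison of the property the product is meant to have. For example, if 25 of 30 DBM patients and 30 of 30 NuCel patients fuse, the named test does not reach significance. Another exact test with the same 5% guarantee does.

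**Working it through.** **Inputs.** Arms of 21 (evaluable target) to 30 (recruited) come from section B; Fisher's test at p < .05 comes from section E. Assumed: a two-sided test, a yes/no fusion outcome, and all fusion rates.

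**The plan's own figure.** No fusion calculation exists to reproduce. The only design figure is 21 per arm for the ODI. With a difference of 0.10 x 52 = 5.2 points, SD 8 and the mean of six measurements with within-patient correlation rho:

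n = 2 (1.960 + 1.282)^2 x 8^2 x [(1 + 5 rho)/6] / 5.2^2

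A single time point needs 50 per arm. At rho = 0.30 the result is 21; at 0.5 it is 30. So 21 is attainable, but rho is not stated. It says nothing about fusion.

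**Step 1: actual size of Fisher's test.** For arms n1 and n2 with a common fusion rate q, sum over all tables (a, b) fused:

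size(q) = sum of C(n1,a) C(n2,b) q^(a+b) (1-q)^(n1+n2-a-b) over tables with Fisher p < .05

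| Evaluable arms | Maximum size over q |
|---|---|
| 21 / 21 | 2.3% |
| 25 / 25 | 3.3% |
| 30 / 30 | 2.7% |
| 21 / 22 | 3.6% |
| 29 / 30 | 3.6% |
| 22 / 27 | 4.4% |

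Over all equal arms from 21 to 30 the maximum lies between 2.3% and 3.3%. At 30 per arm the size is 0.9% when the true rate is 90%.

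**Step 2: the alternative.** Take the two-sided Fisher p-value, pF, as the ordering statistic:

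p(a,b) = maximum over q of Pr(pF of a random table <= pF(a,b))

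Fisher's test is itself valid, so Pr(pF <= c) <= c for every c. Hence this p-value is never larger than Fisher's, and every Fisher rejection is kept. Rejecting at 5% holds the error at or below 5% by construction: the maximum size is 4.8% at 21 per arm and 4.7% at 30.

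**Step 3: one table by hand.** For 25/30 against 30/30, Fisher p = 2 x C(30,5)/C(60,5) = 2 x 142,506/5,461,512 = 0.052. The ordered Boschloo p is 0.027. This is a boundary case: for 24/30 against 30/30 Fisher already gives 0.024.

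**Step 4: power (assumed rates, DBM first).**

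| Arms | Rates | Fisher | Ordered Boschloo |
|---|---|---|---|
| 21 / 21 | 70 vs 90% | 26% | 36% |
| 21 / 21 | 80 vs 95% | 18.5% | 23.7% |
| 30 / 30 | 70 vs 90% | 37% | 43% |
| 30 / 30 | 80 vs 95% | 24% | 33% |
| 30 / 30 | 85 vs 98% | 18% | 31% |
| 29 / 30 | 80 vs 95% | 34% | 44% |
| 29 / 30 | 85 vs 98% | 29.3% | 44.9% |

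The last row is the largest gain found (15.6 points). At 80 vs 95% the gain is nil for arms of 21/22, 25/27 and 26/29, and about 1 point at 23 or 24 per arm.

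**Step 5: the version matters.** A common software default (scipy's two-sided Boschloo) doubles a one-sided p-value. It agrees with the ordered version when arms are equal but not otherwise. For 23/27 against 29/29, Fisher gives 0.048 and the doubled version 0.052, so a Fisher rejection is lost. With 27 DBM and 29 NuCel patients at 85 vs 98%, power is 40% for Fisher and 29% for the doubled version.

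**The case against.** The strongest reply is that nothing here is wrong. A threshold of p < .05 does not promise an actual size of 5%. Fisher's test keeps the error below 5% and is conventional in small samples. Fusion is not the primary outcome, and its comparison is conditional. All of this stands.

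Four stronger readings are tempting, and the documents do not support them:

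- *That the true error never reaches 3% at 21 to 30 per arm.* It reaches 3.3% at 25 per arm, and about 3.6% once a single patient is missing from one arm (29 against 30). Section B plans for losses, so exactly equal evaluable arms cannot be assumed.
- *That the result holds however fusion is defined.* The figures need a yes/no cut, which section C does not give. A 2x3 Fisher test on the three grades has size 3.3% to 4.7% for most grade mixes tried, and about 1.5% when 90% of patients share one grade.
- *That any Boschloo test dominates Fisher.* Only the version ordered by the two-sided Fisher p-value does so.
- *That the choice of test is why fusion would be poorly powered.* At 70 vs 90% the better test still reaches only 36% to 43%, because the trial was sized for the ODI.

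What remains is that, if the comparison is run, Fisher is the only test named for the stated goal. A test with the same guarantee and at least the same power is available.

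**Conclusion.** The point holds as an efficiency improvement. Fisher's test uses at most about 2.3% to 3.3% of the allowed 5% with equal evaluable arms of 21 to 30, and about 3.5% to 4.4% for the unequal splits checked. The ordered Boschloo test gains from 0 to about 15 percentage points of power and never loses any. These figures rest on a two-sided test, a yes/no fusion outcome, and fusion rates that are assumptions throughout. The gain cannot be known in advance, because it depends on how many patients in each arm have a readable CT.

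A reader might infer that the plan misstates its error rate or that its fusion analysis is invalid. Neither follows: the planned test is valid, and the comparison is secondary and conditional. The undefined sample-size condition, the missing cut and the absence of any power statement for fusion limit that analysis more than the choice of test does.

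**What to change.** In section E, before any CT result is seen by arm, replace the Fisher test with wording such as: *Fusion (yes/no, defined as [stated cut of the three CT grades]) will be compared at 6 and 12 months by two-sided Boschloo unconditional exact tests, with tables ordered by the two-sided Fisher p-value.*

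The ordering statistic must be written out, and a doubled one-sided version ruled out, for the reason shown in step 5 of the working.

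The cost is one sentence, a few lines of code to enumerate the tables, and a less familiar test name. No patient, scan or visit is added.
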